7.7 Additional LITT Procedure(s)

If a subject undergoes an additional LITT MTLE procedure for persistent seizures, the following evaluations and CRFs will be completed:

- *Neuropsychological Testing* CRF (testing must be completed prior to the procedure)
- Evaluation CRF (for an unscheduled (Discharge) visit)
- LITT Procedure CRF

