LITT Treatment				✓														
MRI					✓	✓								✓				
Surgical pain VAS						✓	✓											
Surgical outcome classifications ³										✓		✓		✓				✓
Subject satisfaction												✓						✓

Abbreviations: C; collect; D; dispense; DC; discharge; I; initial; LITT; laser interstitial thermal therapy; Mo.; month; MRI; magnetic resonance imaging; QOLIE-31; Quality of Life in Epilepsy - 31; U; update; VAS; visual analog scale.

¹ See Appendix A for details of the neuropsychological testing at each visit. These can be performed on a separate day than the study visit, as long as it is completed within the study window.

² Prior neuropsychological testing may be used for baseline values if the testing was conducted within 6 months prior to the specific baseline visit and there were no significant changes to the subject's AEDs or changes to the subject's clinical condition that may affect cognitive function.

³ See Appendix B for details about the Engel and ILAE surgical outcome classifications.

Table 2: Visits and Testing Requirements and Data Collection Summary (Month 13 through Month 24)

	Months 13, 14, 15, 16, & 17	Month 18	Months 19, 20, 21, 22, & 23	Month 24	Early Withdrawal
Visit Window	± 7 days	± 14 days	± 7 days	± 14 days	
Visit Type					
QOLIE-31		✓		✓	✓
Medication review (epilepsy and non-epilepsy)	✓	✓	✓	✓	
Neurological exam		✓		✓	✓
Functional assessment		✓		✓	✓
Seizure diary	C/D	C/D	C/D	C	
Adverse event monitoring	✓	✓	✓	✓	✓
Surgical outcome classifications ¹		✓		✓	✓
Subject satisfaction		✓		✓	✓
Neuropsychological testing ²					✓

Abbreviations: C; collect; D, dispense; QOLIE-31, Quality of Life in Epilepsy - 31; U, update.
¹ See Appendix B for details about the Engel and ILAE surgical outcome classifications.
² See Appendix A for details of the neuropsychological testing.

9 Sample Size

For this feasibility study, there are no hypothesis tests and therefore sample size is not based on power. Rather, the sample size of 30 subjects is based on providing a sufficiently robust characterization of adverse events and other study endpoints. With a sample size of 30 subjects, adverse events that have a 5% probability per-subject have approximately an 80% chance of being observed in at least one subject in the study. Study results obtained from a sample of 30 subjects will permit planning for the potential range of results that could occur in a larger pivotal trial.

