Up to 45 subjects will be enrolled at up to 8 sites in the United States to ensure that approximately 30 subjects undergo the LITT procedure. It is expected that each site will enroll no more than 10 subjects to ensure that all sites have an opportunity to contribute data to the study and to prevent any one site from having an outsized influence on the overall results of the study.

10 Analysis Populations

The following analysis populations are defined:

- **Enrolled Set:** All subjects enrolled in the study
- **Treated Set:** All subjects that received thermal delivery with the NBS
- **Per-protocol Set:** A subset of the Treated Set that does not have a protocol deviation (see below)

In the feasibility study setting, conclusions about performance are best informed by analyses of the Treated Set. Analyses may be repeated on the Enrolled Set for full reporting of study results and on the Per-protocol Set to provide insight into the potential impact of protocol deviations on the analysis results.

The Per-protocol Set will exclude subjects with protocol deviations that seriously affect the integrity of the data. The deviations that will result in subject data being excluded from the Per-Protocol Set are:

1. Subject did not meet the following study inclusion criteria:

- Diagnosis of unilateral medial temporal lobe epilepsy (MTLE) confirmed clinically and with either (1) ictal scalp recording and MRI evidence of mesial temporal sclerosis or (2) intracranial ictal onset consistent with hippocampal origin.
- Subject or legally authorized representative is able to provide appropriate consent to participate.
- Subject averages 3 or more complex partial seizures (with or without secondary generalization) per month over the 3 most recent consecutive months prior to baseline.

2. Subject should not have undergone the study procedure (i.e. subject was found not to have met the treatment eligibility criteria in Section 6.4 of the clinical study protocol)

Protocol deviations may be reviewed prior to performing analysis of study outcomes to identify deviations, in addition to those identified above, that may result in excluding a subject from the per-protocol set. Reviewing protocol deviations prior to analysis of outcomes is intended to prevent bias in the analysis results while still allowing for identification of significant protocol deviations that could impact outcomes but that were not anticipated at the time that the Statistical Analysis Plan was written.

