11.1 Endpoint Analysis

Since the objective of this feasibility study is to characterize the performance of LITT, no formal hypotheses tests are planned for any endpoint. Descriptive statistics and exploratory analyses will be used in reporting outcomes for all endpoints.

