11.1.3 Secondary Endpoint: Analysis of Seizure Outcomes

Surgical outcome classification will be reported by tabulating the Engel and ILAE class frequency distribution at each scheduled follow-up, among subjects completing that follow-up visit. The change in surgical classification between visits may be described by performing a cross-tabulation of the classifications at subsequent visits. The classifications are described in more detail in Appendix B.

For the Engle classification, there are several classification terms that can be subjective in nature, so further definitions are provided to the sites, as follows:

- the term “disabling seizures” includes all focal seizures *except*
 - those without impairment of consciousness or responsiveness (simple partial seizures) involving subjective sensory or psychic phenomena only
- The term “worthwhile improvement” is defined as $\geq 50\%$ seizure reduction compared to baseline.

Seizure frequency will be characterized by calculating the rate of seizure occurrence within specific follow-up time periods (count of reported events/reported time frame). Follow-up time periods of interest include all follow-up and between-visit follow-up periods (e.g., procedure to Month 3) to characterize the longitudinal course of seizure frequency. For each time period, descriptive statistics of subject-specific rates characterize the distribution of observed seizure rates. The change from baseline in seizure rates may also be calculated by calculating the difference in rate between a follow-up period and the baseline rate of seizures occurring prior to treatment (count of reported events/reported time frame). Since subjects may have different baseline seizure rates, the relative change from baseline in the event rate (r)

$$\frac{(r_{\text{follow-up}} - r_{\text{baseline}})}{r_{\text{baseline}}}$$

will also be calculated to scale the degree of improvement relative to the baseline rate. These analyses may be repeated for subsets of seizures with specific classifications to characterize the frequency of different seizure types.

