18.1 Medication and Concomitant Epilepsy Treatment

Changes to medications have the potential to impact the study endpoints and may be confounded with the impact of the investigational treatment. The analyses described below can provide insight into the potential impact of medication changes.

1. Subjects that had significant changes to the AED regimen (e.g., dosage change, discontinued AED, or new AED) between the Baseline Week -12 visit and the Month 24 visit will be excluded from analyses of visits after the AED changes occur (data censored after medication change).

Additionally, compare observed (uncensored) results at different follow-up time points between the 4 groups of subjects below. The AED regimen change group is determined by changes that occur prior to the follow-up time point being evaluated.

- (a) No change in AED regimen (same medications and dosage compared to baseline)
- (b) Increase in AED regimen (increased number of medications or dosage compared to baseline)
- (c) Decrease in AED regimen (decreased number of medications or dosage compared to baseline)

(d) Other AED regimen change (increased dosage of a medication or addition of a new medication and decreased dosage or discontinuation of a different medication compared to baseline)

2. Subjects that had clinically significant changes to other concomitant epilepsy treatment (e.g., other surgical procedures, vagal nerve stimulation) between the Baseline Week -12 visit and the Month 24 visit will be excluded from analyses of visits after the changes to concomitant epilepsy treatment occur (data censored after concomitant epilepsy treatment change).

19 Poolability of Data

This study is designed and conducted as a multicenter clinical trial. All participating sites will be selected using the same criteria and trained prior to enrolling subjects. All subjects will be treated and evaluated following the same protocol to ensure generalizability of the study results. Poolability of the data across centers in a multicenter study is assumed without burden of proof.

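### The visit-based outcomes have no rule for repeat LITT or other epilepsy surgery, and neither planned version counts re-treatment as failure of the index ablation

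*SAP*

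**What the plan says.** Protocol 7.7 provides for a second ablation: "If a subject undergoes an additional LITT MTLE procedure for persistent seizures, the following evaluations and CRFs will be completed". It lists neuropsychological testing and forms to complete, and no analysis rule.

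The SAP does not mention repeat LITT. Its section 10 says that "conclusions about performance are best informed by analyses of the Treated Set", and no exclusion or failure rule applies after re-treatment. Section 11.1.3 plans for "tabulating the Engel and ILAE class frequency distribution at each scheduled follow-up, among subjects completing that follow-up visit". Interval seizure rates and 3-month responder status (11.1.3), and the proportion with a 13-point QOLIE-31 change (11.1.4), are likewise taken as they stand at each visit or interval.

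The one analysis directed at other surgery is SAP 18.1 item 2. It gives other surgical procedures and vagal nerve stimulation as examples and states that the subjects concerned "will be excluded from analyses of visits after the changes to concomitant epilepsy treatment occur". The opening of section 18 makes sensitivity analyses permissive, not required. Worst-case imputation in section 17 is written for missing data, and a re-treated subject who attends visits is not missing.

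**The concern.** By the protocol's own description, repeat LITT follows persistent seizures, so it is a sign that the index ablation did not do what was intended. Dropping such a subject from later visits is therefore exclusion for a reason linked to outcome. Keeping the subject with the result of the second operation attributes that result to a programme of one or more procedures, not to a single ablation.

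Both are recognised ways to handle re-treatment. The difficulty is that, for binary outcomes, neither can fall below the figure that counts re-treatment as failure. A reader who sees the two agree may take this as support for a single-ablation success rate that neither one estimates.

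The stakes are in planning. SAP section 9 says the results are to help plan a larger pivotal trial, and section 12.7 names 24 months as a time point of primary interest. Any re-treatment during follow-up will have happened by then.

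**Working it through.** **The plan's own figure.** SAP section 9 states that "adverse events that have a 5% probability per-subject have approximately an 80% chance of being observed in at least one subject in the study". With n = 30 and p = 0.05, 1 − 0.95^30 = 0.785, which agrees with about 80%. It has no bearing on this point beyond fixing n at 30.

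**General result for a binary outcome.** Let N be the treated subjects with a visit, b the successes without re-treatment, k the re-treated, and s the re-treated who then succeed.

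- Counted as observed: (b + s)/N
- Removed: b/(N − k)
- Counted as failure: b/N

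Since s ≥ 0 and k ≥ 0, the first two are never below the third. Removal exceeds crediting when b/(N − k) > (b + s)/N. This rearranges to s/k < b/(N − k): the re-treated succeed less often than the others.

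**Illustration.** N = 30 is from the SAP. The values b = 15, k and s are assumptions, because the documents give no re-treatment rate or outcome.

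| k | s | As observed | Removed | Failure |
|---|---|---|---|---|
| 1 | 0 | 15/30 = 50.0% | 15/29 = 51.7% | 15/30 = 50.0% |
| 1 | 1 | 16/30 = 53.3% | 15/29 = 51.7% | 50.0% |
| 3 | 3 | 18/30 = 60.0% | 15/27 = 55.6% | 50.0% |
| 6 | 3 | 18/30 = 60.0% | 15/24 = 62.5% | 50.0% |
| 6 | 6 | 21/30 = 70.0% | 15/24 = 62.5% | 50.0% |

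For k = s = 3 the Clopper-Pearson 95% intervals are 40.6–77.3%, 35.3–74.5% and 31.3–68.7%.

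**Kaplan-Meier.** The event is the first altered-awareness seizure in the diary, ignoring the first 4 weeks. If one precedes re-treatment, the subject is already an event and later handling cannot change that. In an example with 12 events among 30, the 24-month estimate is 18/30 = 60% under every rule. A difference arises only if re-treatment follows no qualifying seizure. Suppose 3 of those 12 are such subjects. Credited, the estimate is 21/30 = 70.0%. Counted as failure it is 18/30 = 60.0%. Censored at re-treatment, with 4 of the other 9 events before that date and 5 after, it is (26/30) × (18/23) = 67.8%.

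**Engel Class I.** IA and IB are defined over the whole time since surgery, and IC needs two years free of disabling seizures. Take a subject with a disabling seizure after day 28, an in-window Month 24 visit (± 14 days), and the clock running from the index procedure.

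- Calendar months: at most 730 + 14 − 28 = 716 days free, below 730.
- SAP study months of 28 days (12.3): at most 24 × 28 + 14 − 28 = 658 days free, below two study years of 2 × 336 = 672.

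Such a subject cannot reach Class I by Month 24. The SAP does not say whether the clock restarts at a second procedure. ILAE class 1, unlike 1a, is not tied in the table to the time since surgery.

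**The case against.** The strongest case on the other side has five parts.

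- **Some analyses already register the failure.** A reader might infer that no planned analysis counts a re-treated subject as a failure. The documents do not support that. The Kaplan-Meier analysis will be reported, with 24 months of primary interest, and it counts anyone who had a qualifying seizure before re-treatment. Visits and intervals before re-treatment also stay in every analysis, and the all-follow-up seizure rate includes those seizures. This stands, and it confines the point to visit- and interval-based results after re-treatment.
- **Engel Class I is largely protected.** A reader might infer that re-treated subjects inflate the Class I rate. The working shows they generally cannot unless the clock restarts, and nothing says it does. SAP 11.1.1 times adverse events from the initial LITT procedure. What remains is that the clock is not stated for the classifications.
- **Removal under 18.1 is an inference.** Repeat LITT is not named there and the analysis is optional. This stands, but if repeat LITT falls outside item 2, no sensitivity analysis addresses it at all.
- **Removal need not raise the rate further.** It exceeds the as-observed figure only when the re-treated do worse than the rest; if all succeed, it lowers it. This stands, but removal still does not fall below the failure figure.
- **This is a small descriptive study.** The SAP says that "no formal hypotheses tests are planned for any endpoint", and the primary endpoint is safety. This limits the weight of the point, but the descriptive proportions are what will be carried into later planning.

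**Conclusion.** The point holds for ILAE class, 3-month responder status, interval seizure rate and the 13-point QOLIE-31 change. The SAP has no rule for repeat LITT or other epilepsy surgery in these analyses. For the binary outcomes, the as-observed and excluded versions both give a proportion equal to or above the one that counts re-treatment as failure.

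The size is unknown. With 30 subjects, each re-treated success adds 3.3 points to the as-observed figure. Under the assumed base of 15/30, the excess when all re-treated subjects do well is 3.3 points for one, 10 for three and 20 for six. Exclusion adds 1.7, 5.6 and 12.5 points. With one re-treated subject the matter is minor.

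The inequality is a property of proportions. For continuous summaries (interval seizure rate, mean QOLIE-31) there is no such bound, only the same absence of a rule. The Kaplan-Meier analysis is largely unaffected. Engel Class I is in general affected only if the clock restarts. That outcomes count as observed after re-treatment is read from the SAP's silence; it is not stated.

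**What to change.** Keep the main analysis and the censored analysis, and amend the SAP as follows.

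1. In 18.1 item 2, name repeat LITT and other epilepsy surgery explicitly.
2. Report the number of subjects re-treated.
3. State that the time since surgery in the Engel and ILAE classifications runs from the index procedure.
4. Add one pre-specified version for binary outcomes. From the date of re-treatment the subject stays in the denominator as not Engel I, not ILAE 1–2, a non-responder, and without a 13-point QOLIE-31 gain.

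Do not carry forward seizure rates or QOLIE-31 scores from before re-treatment. That would impose a strong assumption the documents do not support, and the binary version already answers the question.

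The cost is SAP wording, one extra table version and possibly a slightly less favourable success rate. Nothing in the conduct of the trial changes. The SAP cites protocol Revision A and the current protocol is Revision B, so the wording can go into the same update.

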APPENDIX A NEUROPSYCHOLOGICAL TESTING

This study will include a core neuropsychological battery as well as a supplementary battery, which are described in detail in the study protocol and listed in the tables below. The tests differ based on a subject's spoken language.

Table 3: Neuropsychological Testing Requirements for English-Speaking Subjects

Test	Baseline Week -12	Baseline Week -4	Month 3	Month 6	Month 12	Early Withdrawal
CORE						
WAIS-IV	X				X	X
RAVLT		X			X	X
BNT-60		X			X	X
COWAT		X			X	X
Animal Naming		X			X	X
Trail Making		X			X	X
Grooved Pegboard		X			X	X
Supplementary						
Logical Memory		Form 1	Form 2	Form 3	Form 1	
Auditory Naming		Form 1	Form 2	Form 3	Form 1	
Visual Naming		Form 1	Form 2	Form 3	Form 1	
Verbal Fluency		Form 1	Form 2	Form 3	Form 1	

Table 4: Neuropsychological Testing Requirements for Spanish-Speaking Subjects

Test	Baseline Week -12	Baseline Week -4	Month 3	Month 6	Month 12	Early Withdrawal
Core						
Raven's Matrices	X				X	X
WHO-UCLA AVLT		X			X	X
Ponton-Satz BNT		X			X	X
COWAT		X			X	X
Animal Naming		X			X	X
Color Trails		X			X	X
Grooved Pegs		X			X	X

APPENDIX B SURGICAL OUTCOME CLASSIFICATIONS

The two surgery outcome classifications used in this study, the Engel system,² and ILAE system,³ are presented in Table 5 and Table 6.

The occurrence of early postoperative seizures or auras in the first week after epilepsy surgery is relatively common and may result from the effects of the acute surgical injury (termed “neighborhood” seizures). As such, both the Engel class I and the ILAE class 1 exclude “early” seizures. The Engel classification is not specific for the exact time period (first few weeks postoperative), whereas the ILAE classification excludes seizures in the first 4 weeks. *For the purposes of this study, seizures occurring in the first 4 weeks postoperative will be excluded when evaluating both the Engel and ILAE classes.*

An additional ILAE classification, 1a, is available for those that have been seizure- and aura-free since surgery (as recommended by Wieser et al).

Table 5: Engel Classification

Class I: Free of disabling seizures
A: completely seizure-free since surgery
B: non-disabling simple partial seizures only since surgery
C: some disabling seizures after surgery, but free of disabling seizures for at least 2 years
Class II: Rare disabling seizures ("almost seizure-free")
A: initially free of disabling seizures but has rare seizures now
B: rare disabling seizures since surgery
C: more than rare disabling seizures since surgery, but rare seizures for the last 2 years
D: nocturnal seizures only
Class III: Worthwhile improvement
A: worthwhile seizure reduction
B: prolonged seizure-free intervals amounting to greater than half the follow-up period, but not < 2 years
Class IV: No worthwhile improvement
A: significant seizure reduction
B: no appreciable change
C: seizures worse

Table 6: ILAE Classification

Class 1: Completely seizure-free; no auras
Class 1a: Completely seizure- and aura-free since surgery
Class 2: Only auras ¹ ; no other seizures
Class 3: One to three seizure days ² per year; ± auras
Class 4: Four seizure days per year to 50% reduction of baseline seizure days ³ ; ± auras
Class 5: Less than 50% reduction of baseline seizures days to 100% increase of baseline seizure days; ± auras
Class 6: More than 100% increase in baseline seizure days; ± auras

¹ Auras are only counted if they are short in duration and similar or identical to the preoperative auras.

² A “seizure day” (for the purposes of this classification) is defined as a 24-hour period with one or more seizures. This may include an episode of status epilepticus.

³ The number of “baseline seizure days” is calculated by determining the seizure-day frequency during the 12 months before surgery, with corrections for the effects of AED reduction during diagnostic evaluations prior to the index procedure.

² Engel J Jr, Van Ness PC, Rasmussen TB, Ojemann LM. Outcome with respect to epileptic seizures. In: Engel J Jr, editor. *Surgical treatment of the epilepsies*. New York: Raven Press; 1993:609-21.

³ Wieser HG, Blume WT, Fish D, Goldensohn E, Hufnagel A, King D, et al. ILAE Commission Report. Proposal for a new classification of outcome with respect to epileptic seizures following epilepsy surgery. *Epilepsia* 2001;42:282-6.
